6.2 Participant Exclusion Criteria

Patients must not meet any of the following criteria to be eligible for inclusion in this study:

Memorial Sloan Kettering Cancer Center
[name]
[name]

- Any life-threatening illness, medical condition, or organ system dysfunction that, in the opinion of the investigator, could compromise the patient's safety or put the study outcomes at undue risk
- History of human immunodeficiency virus (HIV) unless all of the following criteria are met:
 - CD4+ T-cell count ≥ 250 cells/ μ l
 - No acquired immunodeficiency syndrome (AIDS)-defining opportunistic infections within 1 year prior to signing Informed Consent form
 - Stable (no change in regimen for 4 weeks) and effective antiretroviral regimen, and HIV viral load < 400 copies/ml within 4 weeks prior to signing Informed Consent form
- Hepatitis B or C with detectable viral load requiring antiviral therapy
- Pregnant or lactating
- Known active bacterial, viral, fungal, mycobacterial, parasitic, or other infection (excluding fungal infections of nail beds) at study enrollment, or any major episode of infection requiring treatment with IV antibiotics or hospitalization (relating to the completion of the course of antibiotics) within 2 weeks prior to cycle 1 day 1
- Clinical significant history of liver disease, including viral or other hepatitis, current alcohol abuse, or cirrhosis
- Active central nervous system lymphoma
- Patients who, in the opinion of the investigator, have not recovered sufficiently from adverse effects of prior therapies
- Documented refractoriness to lenalidomide, defined as no response (PR or CR) within 6 months of therapy
- Lenalidomide exposure within 12 months prior to Day 1 of Cycle 1
- History of hypersensitivity to compounds of similar biological or chemical composition to tafasitamab, lenalidomide, and/or excipients contained in the study drug formulations
- Autologous stem cell transplantation (ASCT) within 3 months prior to signing the Informed Consent form. Patients with more distant history of ASCT must exhibit full hematologic recovery before enrollment into this study.
- Allogeneic stem cell transplantation within 3 months prior to signing the Informed Consent form, with evidence of graft-versus-host disease (GVHD), or receiving immunosuppressive therapy for GVHD.
- Concurrent use of other anticancer or experimental treatments
- No concurrent malignancy requiring active therapy within the last 3 years with the exception of basal cell carcinoma limited to the skin, squamous cell carcinoma limited to the skin, carcinoma in situ of the cervix or breast, adequately treated lentigo maligna melanoma, or localized prostate cancer. Adjuvant or maintenance therapy to reduce the risk of recurrence of other malignancy previously treated for curative intent is permitted.
- Administration of a live vaccine within 28 days prior to the start of study treatment (Cycle 1 Day 1).

7.0 RECRUITMENT PLAN

The study will be conducted at MSKCC. Patients will be treated by members of the lymphoma service at MSKCC. Every effort will be made to include women and minorities in this study. Patients will be recruited by the treating team of physicians and medical professionals. The consenting attending physician will inform patients of their diagnosis, current treatment options including standard treatment, and the risks, benefits, and experimental nature of this treatment program. All patients will be required to sign an Informed Consent form that conforms to FDA and MSKCC IRB guidelines.

7.1 Research Participant Registration

Eligibility will be confirmed as defined in section 6.0 Criteria for Participant Eligibility. Informed consent will be obtained by following procedures defined in section 8.0 Informed Consent Procedures. During the registration process registering individuals will be required to complete a protocol specific Eligibility Checklist. The individual signing the Eligibility Checklist is confirming whether the participant is eligible to enroll in the study. Study staff are responsible for ensuring that all institutional requirements necessary to enroll a participant to the study have been completed. See related Clinical Research Policy and Procedure #401 (Protocol Participant Registration).

8.0 INFORMED CONSENT PROCEDURES

Before protocol-specified procedures are carried out, consenting professionals will explain full details of the protocol and study procedures as well as the risks involved to participants prior to their inclusion in the study. Participants or their legally authorized representatives (LARs) will also be informed that they are free to withdraw from the study at any time. All participants/LARs must sign an IRS/PB-approved consent form indicating their consent to participate.

The consent form/research authorization meets the requirements of the Code of Federal Regulations and the Institutional Review Board/Privacy Board of this Center. The consent form will include the following:

1. The nature, objectives, potential risks, and benefits of the intended study.
2. The length of study, what it entails, and the likely follow-up required.
3. Alternatives to the proposed study. (This will include available standard and investigational therapies. In addition, patients will be offered an option of supportive care for therapeutic studies.)
4. The name of the investigator(s) responsible for the protocol.
5. The right of the participant to accept or refuse study interventions/interactions and to withdraw from participation at any time.

6. How the participants' data will be protected, who will have access to their PHI, and what data will be disclosed for research purposes

Prior to inclusion in the study and before protocol-specified procedures are carried out, the consenting professionals will explain the details of the protocol as outlined in the consent and research authorization to the participants/LARs. The participant/LAR will also be informed that they are free to withdraw from the study at any time. The consent discussion may occur in person or remotely via teleconference, telephone, or videoconference.

All participants/LARs must sign an IRB/PB-approved consent form/research authorization indicating their consent to participate. Each participant/LAR and consenting professional will sign and date the consent form. The participant/LAR must receive a copy of the signed informed consent form.

9.0 PRE-TREATMENT/INTERVENTION

9.1 Pre-treatment/intervention evaluations

All study-related evaluations and interventions are summarized in Section 11.0, Table 11-1.

Within 6 weeks prior to initiating study treatment:

- Pathologic confirmation of R/R MCL, with repeat biopsy prior to initiation of study treatment preferred
- Tumor genomic profiling on MSKCC protocol 12-245 (Integrated Mutation Profiling of Actionable Cancer Targets (IMPACT)) within 6 months prior to signing Informed Consent form, and preferably repeated for patients who did not have IMPACT performed after discontinuing their last line of treatment

Within 4 weeks prior to initiating study treatment (SOC, unless indicated otherwise):

- Physical exam, vital sign measurements, height and weight measurements, and assessment of KPS
- CT scans of chest, abdomen, and pelvis and FOG-PET scan for pretreatment staging (can include CT neck if appropriate per physician discretion)
- **BM** aspiration/biopsy
- Documentation of concomitant medications, including prescription drugs, over-the-counter drugs, herbal products, and supplements/medical foods
- Allergies
- Laboratory testing:
 - Hepatitis B virus (HBV) surface antigen (HbsAg) and core antibody (HbcAb); if either is positive, HBV viral load
 - Hepatitis C virus antibody
 - HIV 1/2 antibodies
- Enrollment in the [Revlimid/lenalidomide REMS program](#)

- Pregnancy testing according to Revlimid/lenalidomide REMS requirements if applicable
- OPTIONAL: fine needle aspirate or other biopsy of involved peripheral nodal tissue (paired with cycle 1 day 22 follow-up biopsy- see Table 11-1)

Within 1 week prior to initiating study treatment (SOC, unless indicated otherwise):

- Laboratory testing:
 - Complete blood count (CBC) with differential
 - Comprehensive metabolic panel (CMP)
 - Phosphorus
 - Uric acid
 - Lactate dehydrogenase (LOH)

9.2 Concomitant therapy

9.2.1 Permitted concomitant therapies

- Standard therapies for concurrent medical conditions
- Inactivated vaccines (eg, injectable influenza vaccine)
- Herbal product and supplement use is discouraged (with the exception of medicinal cannabis administered under the direction and monitoring of an appropriately credentialed health care provider) but not prohibited, provided the given product(s) do not, in the opinion of the investigator, place the patient's safety and/or study outcomes at undue risk
- Antimicrobial prophylaxis
- Palliative and supportive therapies, including but not limited to:
 - Prophylactic and as-needed use of antiemetics
 - Use of granulocyte colony stimulating factor (G-CSF) for prophylaxis or treatment of neutropenia
 - Short-term systemic corticosteroid use, including as antiemetic prophylaxis or management of acute conditions

9.2.2 Prohibited concomitant therapies

- Other investigational and antineoplastic therapies
- Live vaccines
- Immunosuppressive therapies other than corticosteroids as described in 9.2.1

9.2.3 Drug-drug interactions

While lenalidomide is a minor substrate of P-glycoprotein (P-gp), it is not anticipated to have clinically significant interactions with inhibitors or inducers of P-gp.³² Lenalidomide does not undergo phase I or II metabolism, nor is it a known substrate of membrane drug transporters, thus there are no anticipated interactions anticipated when co-administered with cytochrome P450 isozyme or drug transporter inhibitors, inducers, or substrates.

Tafasitamab has not undergone dedicated food-drug or drug-drug interactions. Because its mechanism does not include direct inflammation and it is not extensively hepatically metabolized, it is not anticipated to affect nor be affected by drugs metabolized by, inhibiting, or inducing cytochrome P450 isozymes.

10.0 TREATMENT/INTERVENTION PLAN

10.1 Tafasitamab

Tafasitamab will be administered intravenously according to the [MSK tafasitamab infusion guideline](#) on the following schedule:

- Induction:
 - Cycle 1 (28 days): days 1, 4, 8, 15, and 22
 - Cycles 2 and 3 (28 days each): days 1, 8, 15, and 22
 - Cycles 4 through 12 (28 days each): days 1 and 15
- If SD, PR, or CR after cycle 12, maintenance:
 - Cycles 13-36 (28 days each): day 1

The dose of each tafasitamab infusion is 12mg/kg according to total (actual) body weight. Dose rounding will be performed according to institutional standard. No dose reductions of tafasitamab will be permitted.

10.2 Lenalidomide

Lenalidomide will be self-administered by patients orally on days 1-21 of each 28-day cycle of induction (cycles 1 through 12). Patients will be instructed to take each dose of lenalidomide at about the same time each day with approximately 8 ounces (240ml) of water, without regard to food. Lenalidomide must be swallowed whole; patients should not open or break the capsules. If a dose is missed, the dose may be taken if within 12 hours of usual dosing time. If more than 12 hours have elapsed since usual dosing time, the patient should skip the missed dose and take the next dose at the usual dosing time. If a patient vomits after taking a dose, the dose should not be made up.

Research personnel will review the dosing instructions with patients. Patients will be provided with a medication diary and asked to record the drug administration. Patients will be asked to bring any unused drug and empty drug containers to the research personnel at the beginning of each cycle. Site staff will count and record the number of used and unused drug at the beginning of each cycle and reconcile their findings with the patient diary.

The daily dose of lenalidomide in patients with normal renal function (CrCl 2: 60ml/min) is 20mg. Renal adjustments are outlined in Table 10-1. In patients with impaired renal function at baseline who qualify for study inclusion (CrCl < 60ml/min but 2: 30ml/min), the daily dose of lenalidomide is 10mg daily, with escalation to 15mg daily permitted after 2 cycles if tolerating treatment in the opinion of the investigator. Patients who subsequently develop severe renal dysfunction (CrCl 30ml/min) after initiation of study treatment may continue treatment with lenalidomide at a reduced dose as noted in Table 10-1. Note that renal

dysfunction resulting from toxicity suspected to be related to tafasitamab and/or lenalidomide (eg, due to tumor lysis syndrome) may warrant interruption and/or discontinuation of either or both drugs, as outlined in Table 10-4.

Table 10-1: Lenalidomide dose adjustment for renal dysfunction prior to or after study initiation		
Cockcroft-Gault CrCl (see Appendix B)	Daily lenalidomide dose (days 1-21 of cycles 1-12)	Note
30ml/min and < 60ml/min	10mg	May increase to 15mg once daily after 2 cycles if tolerating treatment in the opinion of the investigator
Severe renal dysfunction after study treatment initiation*		
< 30ml/min not requiring dialysis	5mg once daily	
< 30ml/min requiring dialysis	5mg once daily; for doses on dialysis days, administer after dialysis	

*CrCl must be 30ml/min to be eligible for participation in the study; dose adjustments for CrCl < 30ml/min apply only to patients who met inclusion criteria, initiated treatment with the appropriate initial lenalidomide dose, and subsequently developed severe renal dysfunction

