10.5.4 Hematologic and other toxicities

Toxicities suspected to be related to study medications will be graded according to CTCAE version 5.0 and managed according to Tables 10-4 and 10-5 below.

Table 10-4: Hematologic and other toxicities suspected to be related to either study medication

Thrombocytopenia grade 3-4	Platelets < 50,000 cells/mcL	Cycles 1 through 3: interrupt both tafasitamab and lenalidomide Cycle 4: interrupt lenalidomide only Obtain CBC every 7 days
	Platelets recover to 50,000 cells/mcL	Provided other criteria for dosing are met (see 10.5.1), resume study treatment. If lenalidomide is being continued, it should be resumed at the next lower dose level. Dose re-escalation is permitted in certain circumstances (Table 10-6).

Neutropenia grade 3-4	ANC < 1,000 (but 500) cells/mcl for 7 days Or ANC < 1,000 cells/mcl with fever 38.5°C (101°F) Or ANC < 500 cells/mcl	Cycles 1 through 3: interrupt both tafasitamab and lenalidomide Cycle 4: interrupt lenalidomide only Obtain CBC every 7 days GCSF use is strongly encouraged
	ANC recovers to 1,000 cells/mcl	Provided other criteria for dosing are met (see 10.5.1), resume lenalidomide. If lenalidomide is being continued, it should be resumed at the next lower dose level. Dose re-escalation is permitted in certain circumstances (Table 10-6).
Other clinically significant toxicities (except those attributable to lenalidomide below)	Grade 3-4	Interrupt the study drug(s) to which the toxicity is suspected to be attributable.
	Resolution to grade :s; 2	Provided other criteria for dosing are met (see 10.5.1), resume previous treatment. If lenalidomide was interrupted and is being continued, it should be resumed at the next lower dose level (Table 10-6)

Table 10-5: Other toxicities suspected to be related to lenalidomide

Thromboembolic events	Grade 3-4	Interrupt lenalidomide dosing Start anticoagulation as per MSK anticoagulation guideline and investigator's discretion
	Resolution to grade :s; 2	Resume lenalidomide at investigator's discretion (maintain dose level)

Allergic reaction or hypersensitivity grade 3-4 (including but not limited to Stevens-Johnson syndrome, toxic epidermal necrolysis, exfoliative or bullous rash, angioedema)	Discontinue lenalidomide permanently
Desquamating (blistering) rash grade 3-4	Discontinue lenalidomide permanently

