10.5.6 Lenalidomide dose reductions for toxicity

If lenalidomide dosing was interrupted during the previous cycle, restarted at the next lower dose level during the same cycle in which it was interrupted, and did not require interruption for the remainder of the cycle, then that reduced dose level will be initiated on day 1 of the next cycle. There will be no more than one dose reduction from one cycle to the next.

A dose reduction of lenalidomide constitutes a 5mg decrease in the daily dose from the previous dose, including in patients who initiate treatment at a decreased dose due to renal dysfunction. Patients who are unable to tolerate the lowest dose of 5mg once daily should discontinue lenalidomide but continue treatment with tafasitamab alone.

Table 10-6: Lenalidomide dose reductions for toxicity		Note
Starting dose	20mg once daily days 1-21 of each 28-day cycle	In patients who required lenalidomide dose reduction for hematologic toxicity early in the treatment course due, in the opinion of the investigator, to bone marrow and/or splenic disease
Dose level -1	15mg once daily days 1-21 of each 28-day cycle	
Dose level -2	10mg once daily days 1-21 of each 28-day cycle	

Dose level -3	5mg once daily days 1-21 of each 28-day cycle	involvement, re-escalation to the previous dose level is permitted
Further reduction indicated	Discontinue	

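### After suspected drug-related renal toxicity, Table 10-1 and Table 10-4 give different lenalidomide doses on resumption (10 versus 15 mg from 20 mg), and no sentence reconciles them

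*Combined protocol and SAP*

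**What the plan says.** Two sets of rules bear on the lenalidomide dose when kidney function is reduced.

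**Renal rule (Section 10.2).** The dose is 20 mg for "The daily dose of lenalidomide in patients with normal renal function". For patients impaired at baseline but eligible, "the daily dose of lenalidomide is 10mg daily, with escalation to 15mg daily permitted after 2 cycles", provided the investigator judges treatment to be tolerated. The table that carries these doses is headed "Table 10-1: Lenalidomide dose adjustment for renal dysfunction prior to or after study initiation", so it also covers decline on treatment, and it draws no line by cause. Patients whose CrCl becomes severely reduced on treatment "may continue treatment with lenalidomide at a reduced dose as noted in Table 10-1", where the entry is 5 mg daily.

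**Toxicity rule (Table 10-4, Section 10.5.6, Table 10-6).** Section 10.2 adds that renal dysfunction thought to be caused by a study drug "may warrant interruption and/or discontinuation of either or both drugs, as outlined in Table 10-4". For grade 3-4 events other than cytopenias, Table 10-4 stops the suspected drug and allows treatment to resume at grade 2 or lower if the other dosing criteria are met: "If lenalidomide was interrupted and is being continued, it should be resumed at the next lower dose level (Table 10-6". Section 10.5.6 makes each reduction 5 mg and adds: "There will be no more than one dose reduction from one cycle to the next".

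**The concern.** The renal rule fixes a dose from the current CrCl. The toxicity rule fixes it from the previous dose. Each is workable alone, but a patient with suspected drug-related renal toxicity falls under both, and the two can give different doses on the day lenalidomide is resumed. The cross-reference in 10.2 does not settle this, because it speaks of stopping treatment and not of the dose at restart.

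What is at stake is consistent dosing in a safety situation. Two treating physicians who both follow the text could give similar patients different doses of a drug whose elimination, as Section 15.3 acknowledges, may be impaired in renal dysfunction. A monitor would have no basis for deciding which of them complied.

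**Working it through.** No power or error-rate calculation is involved. The check is a lookup of the two rules for the same patient, with one worked CrCl.

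**Inputs**
- Starting dose with normal renal function: 20 mg daily, days 1-21 (10.2).
- Table 10-1: 10 mg at CrCl 30 to <60 ml/min; 5 mg below 30 ml/min when this arises on treatment.
- Table 10-4 with Table 10-6 and 10.5.6: one level down on resumption, one level being 5 mg.
- CrCl formula: Appendix B.

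**Step 1: a patient in the 30 to <60 band.** Take a man aged 68 (the median age at presentation in Section 3.0). Assume, for illustration, a calculation weight of 70 kg and a serum creatinine of 2.0 mg/dl.

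CrCl = (140 − 68) × 70 / (72 × 2.0) = 5040 / 144 = 35.0 ml/min.

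**Step 2: the two doses.** Suppose he was on 20 mg, had a grade 3-4 renal event suspected to be drug-related, and has recovered to grade 2 or lower with CrCl 35.
- Table 10-4: 20 − 5 = 15 mg.
- Table 10-1: 10 mg.

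The difference is 5 mg a day, and 15 / 10 = 1.5. Over the 21 dosing days of a cycle this is 21 × 15 = 315 mg against 21 × 10 = 210 mg.

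**Step 3: the one-reduction limit.** Moving from 20 mg to the Table 10-1 dose of 10 mg takes (20 − 10) / 5 = 2 levels. Section 10.5.6 allows one reduction from one cycle to the next. It is headed as covering reductions for toxicity and does not say whether a Table 10-1 adjustment counts.

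**Step 4: the full lookup.**

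| Dose before event | CrCl band (ml/min) | Table 10-1 | One level down | Result |
|---|---|---|---|---|
| 20 mg | 30 to <60 | 10 mg | 15 mg | differ |
| 20 mg | <30 | 5 mg | 15 mg | differ |
| 15 mg | 30 to <60 | 10 mg | 10 mg | same |
| 15 mg | <30 | 5 mg | 10 mg | differ |
| 10 mg | 30 to <60 | 10 mg | 5 mg | differ |
| 10 mg | <30 | 5 mg | 5 mg | same |
| 5 mg | 30 to <60 | 10 mg | discontinue | differ |
| 5 mg | <30 | 5 mg | discontinue | differ |

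Read mechanically, the rules differ in 6 of 8 rows. A row matters only if both rules apply to the same patient: the event is suspected to be drug-related, was grade 3-4, has resolved to grade 2 or lower, and CrCl is still in a reduced band. The first row is the one on which the point rests.

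**Step 5: is there a tie-breaker?** The resumption criteria in 10.5.1 list neutrophils, platelets and absence of serious organ toxicity, with no CrCl criterion. Table 10-4 does not mention Table 10-1. Table 10-1 does not mention toxicity levels. No sentence ranks one over the other.

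**The case against.** The strongest reply is that the protocol does separate cases by cause. Table 10-4 and 10.5.6 are confined to toxicity, and 10.2 sends drug-related renal dysfunction to Table 10-4. This stands in part. For decline not suspected to be drug-related, only Table 10-1 applies and there is no conflict. For drug-related decline the reference is incomplete, because it says nothing about the dose at restart and does not suspend Table 10-1.

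A second reply is that the body text of 10.2 ties the 10 mg dose to impairment at baseline. The table's own heading, however, extends to the period after initiation. If the narrower reading were intended, the text and the heading would still need to be aligned.

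A reader might also infer more than the documents support:
- **A threefold gap (5 versus 15 mg) below 30 ml/min.** Resumption requires grade 2 or lower and no serious organ toxicity, while the protocol itself calls CrCl <30 severe. It gives no renal grade cut-offs, so this case is not shown to be reachable. Continuing below 30 is also permitted rather than required.
- **That Table 10-1 raises a dose already cut for toxicity.** The 15 mg option depends on the investigator judging that treatment is tolerated. Section 10.5.6 expressly applies 5 mg reductions to patients who started lower for renal reasons. Reading the table as ordering an increase goes beyond its text.
- **That the one-reduction limit forbids the Table 10-1 change.** The text is silent on this and contains no prohibition. Repeat cytopenias within one cycle are a separate matter, not a renal one.
- **Loss of patients from the per-protocol analysis.** A major violation is not defined, and that analysis is only supportive.

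**Conclusion.** The point holds in a limited form. For a patient on 20 mg with suspected drug-related grade 3-4 renal toxicity that has resolved to grade 2 or lower, and with CrCl still 30 to <60 ml/min, the protocol states two different resumption doses: 15 mg and 10 mg. It also leaves open whether a renal adjustment counts toward the one-reduction limit. Two stated rules give incompatible answers for one patient, so this is a contradiction and not only missing detail.

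The conclusion assumes that the heading of Table 10-1 means what it says about decline after initiation, and that a patient can meet the grade 2 condition with CrCl in that band. The documents give no cut-offs to confirm or exclude the second assumption. They do not give the number of patients affected. The Simon two-stage figures (19 and 39 patients, 30% versus 50% response) are unaffected. The correction should be made because it concerns safety and costs almost nothing.

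**What to change.** Reconcile Section 10.2 with Table 10-1, Table 10-4, and Section 10.5.6 with Table 10-6, so that together they give one answer to two questions:
- which rule sets the lenalidomide dose on resumption after suspected drug-related renal toxicity when CrCl remains reduced;
- whether a Table 10-1 adjustment counts as a reduction under the one-reduction limit.

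The same statement should appear, or be cross-referenced, in each of these places. The dose itself is for the sponsor's clinicians to decide.

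The cost is a few sentences in a protocol amendment. No new tests are needed, since Table 11-1 already schedules chemistry and weight on day 1 of the induction cycles. Sample size, stopping rule and analysis stay as they are.
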